IRB	Institutional Review Board
ISM	Independent Safety Monitor
MedDRA®	Medical Dictionary for Regulatory Activities
MOP	Manual of Procedures
N	Number (typically refers to subjects)
NDA	New Drug Application
OCTOM	Office of Clinical Trials Operations and Management, NIDCR, NIH
OHRP	Office for Human Research Protections
OFP	Orofacial Pain
PHI	Protected Health Information
PI	Principal Investigator
QA	Quality Assurance
QC	Quality Control
SAE	Serious Adverse Event/Serious Adverse Experience
SC	Subcutaneous (as subcutaneous injection)
SOP	Standard Operating Procedure
TMD	Temporomandibular Disorders
UMB	University of Maryland
UMBSOD	University of Maryland, School of Dentistry
UP	Unanticipated Problem
US	United States
WHO	World Health Organization

PROTOCOL SUMMARY

Title:

Erenumab as a therapeutic approach for the management of painful chronic temporomandibular disorders (TMD).

Précis:

A total of 60 patients (30 per each arm) aged 18-65 years old of either sex, and any race or ethnicity presenting chronic temporomandibular disorders (TMD) will be randomly assigned in a 1:1 parallel, double-blind clinical trial, to receive either Erenumab or placebo. Participants will attend 6 clinic visits (Visit 0-Visit 5) over a period of 21 weeks.

Potential participants will be pre-screened at the Brotman Facial Pain clinic and the Oral and Maxillofacial Surgery Clinic both at the University of Maryland, School of Dentistry or by telephone; those willing to participate will be scheduled for a screening and baseline visit (Visit 0). During this visit potential participants will be evaluated for eligibility and written informed consent will be obtained. The screening and baseline procedures include medical history review, clinical examinations, tests and administration of questionnaires. Instructions will be given for the completion of a Daily Symptom Diary (DSD) and other questionnaires at home or online. Participants who show 80% compliance with the DSD and who meet the pain score (inclusion criteria) after Visit 0 (baseline period), will be randomly assigned to one of two groups either the investigational drug or placebo and will be scheduled for Visit 1.

The study drug is Erenumab 70mg, SC injection. After randomization and on Visit 1, the participant will receive the drug or placebo. This same treatment will be administered once a month for 3 months (3 cycles/12 weeks). The primary end point will be a change in the average pain index score from baseline, representing the mean of daily average pain intensity score values (0-100 scale) derived from Daily Symptom Diaries for 12 weeks (12 weeks treatment).

Secondary end points will be participant ratings of other pain related outcomes, examiner assessment of pain, occurrence of symptoms and adverse events.

Exploratory end points are change of [REDACTED]
[REDACTED] cytokine profiles [REDACTED]

Objectives:	Primary: To investigate the efficacy of Erenumab compared to placebo on the reduction of pain scores in patients with TMD during a 12-week treatment period. Secondary: To determine the efficacy of Erenumab on the proportion of subjects with at least 50% reduction from baseline in mean monthly TMD pain days and to determine the efficacy of Erenumab using functional measures namely, jaw functional limitation, pressure pain thresholds and oral behaviors disability, and emotional functioning. Exploratory: To investigate the efficacy of Erenumab in [REDACTED] cytokine release [REDACTED] [REDACTED]
Population:	60 adults of either sex and any ethnicity between the ages of 18 and 65 years with a diagnosis (According to the Diagnostic Criteria for Temporomandibular Disorders (DC/TMD) for Clinical and Research Applications) of chronic TMD (myalgia +/- arthralgia) and no contraindications for the use of Erenumab will be enrolled from the Brotman Facial Pain Clinic and the Oral and Maxillofacial Surgery clinic from the University of Maryland, School of Dentistry.
Phase:	II
Number of Sites:	University of Maryland, School of Dentistry
Description of Intervention:	Study drug is Erenumab 70mg or an inert placebo will be administered by subcutaneous injection once a month (3 cycles) over a 12-week period.
Study Duration:	36 months

[figure not shown]
Subject 21 weeks

Participation

Duration:

Estimated Time to Complete Approximately 2.5 years (30 months)
Enrollment:

Schematic of Study Design:

2 INTRODUCTION: BACKGROUND INFORMATION AND SCIENTIFIC RATIONALE

2.1 Background Information

Temporomandibular disorders (TMD) are a group of related heterogenous musculoskeletal disorders that affect the temporomandibular joint (TMJ), masticatory muscles, and associated structures [1]. TMD pain commonly can be localized in the muscles of mastication, along the mandible, the pre-auricular area, the ear, the temple area as well as associated with TMJ biomechanics, such as mandibular movements, including chewing, talking, yawning and mouth opening[2].

Pain associated with TMD is one of the most common complaints in the craniofacial and cervical area and the most common non-dental reason why patients seek treatment in the dental office [3, 4]. TMD have an overall prevalence estimated between 5% and 12% [5] and are more prevalent in women [5, 6]. TMD include myalgia, arthralgia, intra-articular disorders and degenerative joint diseases [7]. TMD exert a significant burden on the population affecting the productivity and quality of life [8] and it can also be present with other pain conditions such as lower back pain, fibromyalgia and headache[9, 10].

For some patients, TMD has a tendency to remit or improve pain symptomatology over time [11, 12] but for others, TMD have the potential to become chronic and to lead to persistent dysfunction [13-15]. TMD management should be conservative, reversible and based in evidence based therapeutics [16, 17] and includes a combination of home self-care, physical therapy, pharmacotherapy, oral appliance therapy, and behavioral interventions [2, 18]. Pharmacotherapy includes non-steroidal anti-inflammatory drugs (NSAIDs), corticosteroids, muscle relaxants, benzodiazepines, and some anticonvulsants and antidepressants [18] but clear evidence establishing their efficacy is limited. Gabapentin, and anti-epileptic medication have shown to be superior than placebo in reducing myalgia [19] but dizziness and sedation, often present in this drug class with other important side effects, have been reported with its use [20]. Recently propanonol, a non-selective beta adrenergic receptor antagonist, was shown to reduce TMD myalgia when compared to placebo [21]. However, no medical treatment exists that is approved by the Food and Drug Administration (FDA) specifically for the management of TMD. Therefore, safer, and novel pharmacological therapy protocols are urgently needed to address this unmet medical need with significant social and psychological implications.

The calcitonin gene-related peptide (CGRP) is a pro-inflammatory vasodilating neuropeptide involved in migraine pathophysiology in where CGRP levels increase during a migraine attack [22]. Targeting the CGRP receptor pathway has proven to be effective in migraine therapeutics. Erenumab is a fully human monoclonal antibody that inhibits CGRP pathway and is the first in its class to be FDA approved for the management of migraine as a migraine preventive[23].

TMD and migraine are often co-morbid. The presence of TMD significantly increases the likelihood of any form of headache, particularly migraine and can exacerbate its disability

impact [10, 24-26]. We and others have shown that CGRP is also involved in TMD pathophysiology [27] and we demonstrated that blocking CGRP with a CGRP receptor antagonist in a pre-clinical model of TMD, significantly decreased nociception[28]. The management of chronic TMD inhibiting CGRP pathway with an FDA approved medication that has been proved safe for another indication such as migraine which shares CGRP as a molecular link, would be very promising. Therefore, we have hypothesized that Erenumab - a monoclonal antibody that inhibits CGRP receptor- reduces pain and restores function in patients suffering of chronic TMD. This proposed clinical trial is the first study of this nature, looking at Erenumab as a new pharmacological therapy for patients suffering of chronic TMD.

The study will be a randomized, double blind, placebo-controlled trial comparing Erenumab vs Placebo. Participants will be evaluated for TMD and have other related assessments; blood samples will be collected, and they will need to answer some questionnaires. We are going to assess changes in pain intensity and other pain outcomes related to TMD.

2.2 Rationale

Chronic TMD is a considerable burden and affects significantly the quality of life of the sufferer [8]. Medications such as gabapentin and propranolol have indicated to be beneficial in clinical studies [19, 21], but tolerability and side effects may be present for some patients. Furthermore, the indications of these drugs are for other disorders, so it is unclear their mechanism of action in TMD pathophysiology. Currently there is no medication specifically indicated for the management of TMD based on its molecular pathophysiology. However, there is evidence showing that CGRP has a role in TMD pathophysiology [27] and we demonstrated that targeting CGRP in a preclinical model of TMD decreased nociception [28].

CGRP is a key molecule in migraine pathophysiology. Erenumab is the first antibody therapeutic targeting the CGRP receptor with FDA approval [23]. It has shown efficacy, to be well tolerated and with a safety profile similar to placebo for the prevention of chronic migraine in adults [29-31]. Erenumab is also approved in the prevention of episodic migraine in adults demonstrating its efficacy in randomized controlled clinical trials and has been shown promising for the management post-traumatic headache attributed to brain injury [32, 33]. Migraine and TMD share CGRP as a molecular link [26]. Therefore, the scientific premise for this study is that inhibiting CGRP in chronic TMD will decrease pain, pain related outcomes and improve TMJ biomechanics (function) in a safe and well tolerated manner for this patient population.

2.3 Potential Risks and Benefits

2.3.1 Potential Risks

Use of Erenumab: Erenumab is a fully human monoclonal antibody that inhibits CGRP receptor and is FDA approved for the preventive treatment of migraine in adults. As of 16 May 2020, approximately 6,550 people have received erenumab in research studies. Since it was first approved for sale on 17 May 2018, approximately 423,800 people have been prescribed erenumab (Aimovig®) for treatment as of 16 May 2020.

The safety profile of erenumab has been favorable in clinical trials and in the post-marketing setting. A limited number of adverse drug reactions (injection site reactions, constipation, muscle spasm, and pruritus) have been identified at low frequencies (< 5%) in clinical trials. In the long-term use of erenumab, the safety profile remained consistent through 5 years of open-label treatment. In post-marketing settings, hypersensitivity reactions (including rash, angioedema and anaphylactoid reactions) and constipation with serious complications have been reported. In addition, oral sores (eg, stomatitis, mouth ulceration, oral mucosal blistering), alopecia and rash (eg, rash papular, exfoliative rash, rash erythematous, urticaria, blister) have been observed in post-marketing surveillance

Serious constipation has been reported in patients prescribed erenumab. In some cases, hospitalization or surgery was required. Constipation and the use of medications that decrease gastric motility are in our exclusion criteria, however if a new onset of constipation occurs, the participant will be withdrawn of the study and will be referred to an appropriate practitioner for continued care (see section 9.2).

Hypertension or worsening of high blood pressure can happen after receiving Erenumab. Hypertension is in our exclusion criteria, however if a new onset of hypertension occurs, the participant will be withdrawn of the study and will be the participant will be referred to an appropriate practitioner for continued care (see section 9.2)

After taking erenumab, antibodies against erenumab may be produced; this has been observed in clinical studies. No side effects associated with these antibodies were observed.

Side effects of the use of erenumab in combination with other drugs are unknown at this time.

There are no adequate data on the developmental risk associated with the use of erenumab in pregnant women or breastfed babies. There are no data on the presence of erenumab in human milk, or on milk production. Pregnant women, breastfeeding women and women planning to become pregnant will be excluded from this study. If a participant gets pregnant, decides to breastfeed her baby or father a child while taking erenumab will be withdrawn from the study and will be monitored and referred to an appropriate practitioner for continued care (see section 9.2 and 9.4.1).

Participants will be closely monitored for any AEs, during the clinic visit and between visits by telephone. Potential risks and discomforts will be clearly stated in the ICF.

TMD examination and pressure pain threshold testing (PPT): A TMD examination will assess muscles of mastication and TMJ sensitivity to manual palpation. The PPT will assess pain applying pressure with the use of an algometer in muscles and the TMJs. Both assessments will be performed on 4 clinic visits. It is expected that these assessments will evoke brief pain or discomfort within a range that is acceptable for the participant. Transient redness or tenderness of the skin may appear after these assessments but none of them is expected to result in lasting discomfort or tissue damage. In addition, the participants may request to stop the examination/test at any time. These assessments will end upon the completion of the modality or upon the participant's request, whichever comes first.

Self-care: It is possible that some participants may feel frustrated if they are unable to incorporate and to understand some self-management approaches.

Questionnaires: It is possible that some participants may experience discomfort associated with answering several questionnaires as well as with being asked personal questions about his/her emotional state and feelings, health history or symptomatology. The participants will be informed that they can choose not to answer any question for any reason.

Blood collection: Participants may find the blood draw unpleasant and there is a possibility of mild pain and bruising associated with it. Trained personnel will perform the blood draw using standard procedures. If for any reason the blood draw is being difficult (i.e. finding a vein) and the subject/patient is uncomfortable, the blood draw will be stopped immediately. The participants will be informed that they can choose to stop the blood collection for any reason.

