5.1 Subject Inclusion Criteria

In order to be eligible to participate in this study, an individual must meet all of the following criteria:

1. Provide signed and dated informed consent form
2. Is between 18 and 65 years of age (inclusive; male or female and any race or ethnicity)
3. Meets diagnostic criteria for TMD: Myalgia with or without arthralgia
 - The participant must meet 2 criteria relating: 1) reported pain, ache or tenderness in the face, jaw/mandible, pre-auricular area, inside the ear or temple that it is modified by TMJ biomechanics. 2) finding(s) of TMD myalgia according to the classification DC/TMD criteria.
4. Has experienced facial pain and/or pain with TMJ biomechanics for the last 3 months episodically or unremitting
5. Has experienced facial pain for at least 10 days of the last 30 days prior to Baseline Visit (Visit 0)
6. Prior to randomization, has been compliant 80% with the entries in the Daily Symptom Diary within the baseline period and reported an average pain level ≥ 30 on a numerical rating scale (0-100) in the DSD, or has experienced a pain level ≥ 30 on the same scale for at least 3 days in the week prior to Visit 1.
7. If taking a prescription medication daily for the management of pain (taken for at least 30 days before baseline), agrees to continue the daily use of the medication throughout the study at the same dosage.

8. If taking prescription medication, opioid medication or OTC medications as needed or episodically for the management of TMD pain agrees to discontinue its use prior to the Screening and Baseline Visit.
 - Rescue medications will be defined as allowable over-the-counter analgesics used for treatment of TMD pain. In case a patient presents pain during the study, only it is allowed the use of OTC medications as a “rescue” and as described on section 6.6.3: Participants use of short-acting non-prescription analgesics such as NSAIDs, acetaminophen or aspirin during the study, will be recorded and quantified at each visit, and the usage will be classified as either episodic or daily. Episodic use of non-prescription analgesics will be defined as use for no more than 2 consecutive days and for no more than 18 days from baseline to visit 4.
 - This type of analgesics should not be used for more than 2 days a week prior to Baseline and a week prior to visit 4, when the exploratory outcome is assessed (cytokine release assay).

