5.2 Subject Exclusion Criteria

1. Participants with a history of congestive heart failure, rheumatoid arthritis or uncontrolled diabetes.
2. Participants with serious hepatic, respiratory, hematologic or immunologic illnesses, an unstable cardiovascular disease, or any other severe acute or chronic medical or psychiatric condition or laboratory abnormality that may increase the risk associated with trial participation or Erenumab or may interfere with the interpretation of trial results and, in the judgment of the investigator, would make the participant inappropriate for entry into this trial
3. Participants with high blood pressure, history of abnormal electrocardiograms, history of heart conductance defects, malignant disease, chronic constipation, IBSc or any other severe acute or chronic medical or psychiatric condition or laboratory finding that may increase the risk associated with trial participation with Erenumab
4. Participants with active malignancy of any type or a history a malignancy (with exception of participants with malignancy surgically removed with no evidence of recurrence within 5 years before enrollment).
5. History of facial trauma or orofacial or orthognathic surgery within the previous 6 months
6. Patients with dental pain
7. Patients with trigeminal neuralgia or other neuropathic pain in the craniofacial area
8. Patients with rheumatoid arthritis or any systemic arthritis
9. Patients with chronic migraine with and w/o aura following the ICHD-3 criteria treated or not treated with medication
 - Without excluding headache attributed to TMD

10. Participants currently taking or have previously taken Erenumab or other CGRP monoclonal antibody (mAmb) or currently taking a CGRP-Receptor antagonist (gepants) for migraine prevention. CGRP-Receptor antagonist (gepants) for acute use for migraine are allowed.
11. Patients with hypersensitivity to Erenumab
12. Patients who have received the Botox injection protocol in the masseters and/or Migraine protocol within 3 months prior screening and baseline visit.
13. Used injections for management of TMD (trigger point injections, steroid injections) within 2 weeks prior to the Screening and Baseline Visit
14. Has commenced a new daily prescription medication for the management of pain within 30 days prior to the Screening and Baseline Visit
15. Has commenced intraoral appliance therapy for the management of facial pain within 30 days prior to the Screening and Baseline Visit

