16. Patient currently undergoing active orthodontic treatment (passive retainers are permitted)
17. Treatment for drug or alcohol abuse within the last year
18. Has been treated with another investigational drug or treatment within 30 days prior to the Screening and Baseline Visit
19. Patients sensitive to Latex
20. Patient is pregnant, planning to become pregnant or breastfeeding
21. Anything that, in the opinion of the investigator, would place the participant at increased risk or impede the participant's full compliance with or completion of the study.

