5.4 Treatment Assignment Procedures

This will be a conventional factorial design, randomized, double-blinded clinical trial with two parallel arms to evaluate efficacy of Erenumab:

- Erenumab, a monoclonal antibody medication that inhibits the CGRP pathway, which is FDA-approved for the prevention of migraine in adults. The comparison will be to placebo.

5.4.1 *Randomization Procedures (if applicable)*

Extensive screening procedures of potential participants to determine their eligibility based on the inclusion and exclusion criteria will be carried out prior randomization. Participants who do not meet these criteria will not be enrolled in the study.

Randomization visit will be within 7 days after Visit 0, eligibility will be further confirmed based on completion of Daily Symptom Diaries and pain intensity score. Qualified participants will be randomly assigned to one of the two arms of the study in a 1:1 ratio:

- 1) Investigational arm: Erenumab: N= 30 participants
- 2) Placebo: N=30 participants

Randomization

Subjects will be randomized to the investigational treatment group (Erenumab) or the placebo group using a blocked randomization scheme. The examiners and patients will be blind to the group assignment. Randomization will be done by Investigational Drug Services (IDS/Research pharmacy). There will be a 1:1 ratio of treatment to placebo participants.

Blinding

Blinding will be done by Investigational Drug Services (IDS). The PI and study staff will be blind to what the participant is receiving.

Treatment/randomization codes

IDS will be responsible for randomization of participant assignment to either the study medication or placebo groups. IDS will use a random number generation program to determine assignment.

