6.3 Modification of Study Product Administration for a Subject

If a dose of Erenumab is missed, will be administered as soon as possible. Thereafter, Erenumab will be scheduled monthly from the date of the last dose.

The safety profile of erenumab has been favorable in clinical trials and in the post-marketing setting. A limited number of adverse drug reactions (injection site reactions, constipation, muscle spasm, and pruritus) have been identified at low frequencies (< 5%) in clinical trials. In the long-term use of erenumab, the safety profile remained consistent through 5 years of open-label treatment. In post-marketing settings, hypersensitivity reactions (including rash, angioedema and anaphylactoid reactions) and constipation with serious complications have been reported. In addition, oral sores (eg, stomatitis, mouth ulceration, oral mucosal blistering), alopecia and rash (eg, rash papular, exfoliative rash, rash erythematous, urticaria, blister) have been observed in post-marketing surveillance.

Hypertension or worsening of high blood pressure can happen after receiving Erenumab. Hypertension is in our exclusion criteria, however if a new onset of hypertension occurs, the participant will be withdrawn of the study and will be the participant will be referred to an appropriate practitioner for continued care (see section 9.2).

Participants will be closely monitored for any of these AEs, during the clinic visit and between visits by telephone. Potential risks and discomforts will be clearly stated in the ICF. Exclusion criteria includes medical history of constipation or taking medications associated with decrease of G.I motility as well as pre-existent hypertension (See 5.2). If the participant reports a hypersensitivity reaction (rash, angioedema, anaphylaxis), new onset constipation or new onset of hypertension or any of the reactions described above, if there is worsening of TMD signs and symptoms during the 18 weeks of participation or if the participant decides against using Erenumab, he/she will be discontinued from the study (See 2.3.1 and 5.5.2).

The following expected events will not be considered reportable AEs:

- Temporary injection site reactions such as pain, erythema, pruritus after the injection of Erenumab
- Minor bleeding or bruising resulting from the blood draw
- Temporary pain or temporary increases in existing pain prompted during the TMD clinical examination or PPT.

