7.2 Screening and Baseline Visit (Visit 0, 4 weeks baseline period)

- Obtain and document consent from subject participation in the study.
- Obtain signed Health Insurance Portability and Accountability Act (HIPAA)

Authorization

- Review medical/dental history to determine eligibility based on inclusion/exclusion criteria.
- Take blood pressure and collect weight and height.
- Review medications history to determine eligibility based on inclusion/exclusion criteria.
 - Record concomitant medications and therapies
- Administer Symptom Inventory
- Perform TMD examination (Including Panoramic X-Ray).
- Perform Pressure Pain examination

- Collect blood for Cytokine release assay
- Perform urine pregnancy test (in women with childbearing potential)
- Provide instruction to complete 6 outcome measure questionnaires in paper or electronically for review next visit
- Provide instruction to complete Daily Symptom Diaries electronically or in paper dispense forms.

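### Three sections state that medication slowing gastric or G.I. motility is excluded, but none of the 21 exclusion criteria in section 5.2 names it

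*Combined protocol and SAP*

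**What the plan says.** Section 2.3.1 reports serious constipation in patients prescribed erenumab, with hospital admission or surgery in some cases. The next sentence offers the mitigation: "Constipation and the use of medications that decrease gastric motility are in our exclusion criteria". It adds that new-onset constipation leads to withdrawal. Section 9.3.2 carries the same sentence in its list of post-marketing events. Section 6.3 words it slightly differently and cites 5.2 as the source: "Exclusion criteria includes medical history of constipation or taking medications associated with decrease of G.I motility".

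Section 5.2 is a numbered list of 21 exclusion criteria. The only one that names a bowel problem is criterion 3, which includes "malignant disease, chronic constipation, IBSc or any other severe acute or chronic medical or psychiatric condition". The only one that concerns ongoing prescription pain medicine is criterion 14: "Has commenced a new daily prescription medication for the management of pain within 30 days prior to the Screening and Baseline Visit". Criterion 21 is a general clause: "Anything that, in the opinion of the investigator, would place the participant at increased risk", or would impede compliance or completion.

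Section 5.4.1 makes the lists decisive: "Participants who do not meet these criteria will not be enrolled in the study". At Visit 0, section 7.2 instructs staff as follows: "Review medications history to determine eligibility based on inclusion/exclusion criteria". Inclusion criterion 7 in 5.1 says that a patient on daily prescription pain medicine for at least 30 days before baseline "agrees to continue the daily use of the medication throughout the study at the same dosage". Section 6.6.2 likewise asks that such a regimen be left unchanged.

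**The concern.** The risk section relies on a preventive safeguard that the eligibility list does not contain. A screener works from 5.1 and 5.2, and nothing there tells them to look for motility-slowing drugs or to turn away a patient who takes one. An IRB or safety board member reading 2.3.1 would reasonably believe that such patients cannot enter.

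The protocol itself treats the hazard as real. Section 9.1.3 lists severe constipation that may need hospital admission among the serious adverse events, and 2.3.1 says that the side effects of erenumab combined with other drugs are unknown. A patient already on a motility-slowing drug is one for whom the stated exclusion was meant to matter.

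**Working it through.** No formula applies. The check is to read each statement that the exclusion exists against each place where it could be put into effect.

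**Where the exclusion is claimed: 3 sections.**
- 2.3.1: medication decreasing gastric motility.
- 9.3.2: the same sentence.
- 6.3: medication associated with decreased G.I. motility, citing 5.2.

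**Where it should appear: 5.2.** The list runs from 1 to 21 without a break or redaction, so the gap does not come from removed text.
- Criteria naming motility-decreasing medication: 0 of 21.
- Criteria naming constipation or IBSc as a condition: 1 of 21 (criterion 3).
- Criteria concerning drug or injection treatment: 5 of 21. These are 10 (CGRP antibodies and gepants), 12 (Botox), 13 (injections for TMD), 14 (newly started daily prescription pain medicine) and 18 (investigational treatments). None concerns motility.

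**Where else it might appear.**
- 5.1: 0 of 16 inclusion criteria name it. Criterion 8 stops as-needed or episodic medication for TMD pain, opioids included, before Visit 0. Criterion 10 bars starting new prescription pain medicine during the study.
- 6.6: no motility restriction among the concomitant medication rules.

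**Is this a drafting habit or an omission?** Comparable safety claims do have a counterpart in 5.2. Hypertension and chronic constipation are in criterion 3, latex sensitivity is criterion 19, and pregnancy and breastfeeding are criterion 20. The motility claim has none, which points to an omission.

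**What the rules do with a patient on such a drug.** Take a patient without chronic constipation or IBSc.
1. If the drug is a daily prescription pain medicine of more than 30 days' standing, criterion 14 does not apply, and inclusion 7 and 6.6.2 have the patient continue it.
2. If the drug is taken for something other than pain, neither 5.1 nor 5.2 addresses its effect on motility.
3. If it is an as-needed medicine for TMD pain, inclusion 8 stops it. This is the one route that is covered.
4. If a non-pain drug of this kind is started during the study, section 5.5.1 allows withdrawal when a participant newly meets an exclusion criterion. With no such criterion listed, that ground is not clearly triggered.

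In cases 1 and 2 only investigator judgement under criterion 21 stands between the patient and enrolment.

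**The case against.** The strongest reply is that the sponsor's intent is plain. It is stated three times, so an investigator using criterion 21 is not uninformed, and criteria 2 and 3 also give room for judgement about added risk with erenumab. This helps only in part. Criteria 2 and 3 concern conditions and laboratory abnormalities rather than drugs. Criterion 21 leaves to opinion what the risk text presents as a fixed exclusion. None of the three sections gives drug classes or a time window that a screener could apply.

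A second reply is that the exposure is small. Section 2.3.1 puts constipation among reactions seen in under 5% of trial participants and attributes constipation with serious complications to post-marketing use. With 30 people on erenumab, 5% would be 0.05 × 30 = 1.5, so fewer than 1.5 cases of any grade would be expected. That figure is fair as background. It does not describe users of motility-slowing drugs, for whom the documents give no rate.

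A third reply is that other protections exist. Chronic constipation and IBSc are excluded, inclusion 8 and 10 limit pain medicines, new-onset constipation means withdrawal, and there are calls between visits and on the evening of each injection. A symptom inventory and a medication review also take place at the visits. All of this stands. The exclusions and medication limits leave stable daily pain medicines and non-pain drugs uncovered. The withdrawal rule, calls and symptom inventory act only once symptoms have begun.

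Finally, the case report forms or the Manual of Procedures, which were not available for this review, may carry the item. The Supplemental Materials page says those documents are not part of the protocol and can be changed without an amendment, so they cannot supply a missing criterion.

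**Conclusion.** The concern holds. The exclusion is claimed in 3 sections and appears in 0 of 21 exclusion criteria and 0 of 16 inclusion criteria. The protocol is wrong as written: either 5.2 is incomplete or the three safety statements are untrue.

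The conclusion rests on the text alone and on reading 5.1 and 5.2 as the operative eligibility test, which 5.4.1 and 7.2 support. How many candidates take such medication, and how much it adds to the risk of constipation, are not given, so no patient count is offered. Sample size, power, randomisation and the primary analysis are unaffected. It should be fixed because a safeguard against a recognised serious harm is asserted but not put into effect, and the repair is cheap.

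**What to change.** Add a criterion to 5.2 excluding current use of medication that decreases gastrointestinal motility. The medical monitor should list the drug classes and set the period before Visit 0 during which use counts. The Visit 0 medication review would then screen these patients out, and the existing withdrawal ground in 5.5.1 would cover a participant who starts such a drug later. A short cross-reference in inclusion 7 and in 6.6.2 would prevent those passages being read as permission to continue one.

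If the medical monitor decides that the exclusion is not needed, remove the medication claim from 2.3.1, 6.3 and 9.3.2, and from any other risk text that repeats it.

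Either route costs one protocol amendment with IRB approval under 15.2. The first also loses some candidates at screening. The documents do not give that number, or say whether the planned 300 screened for 60 randomised (300 / 60 = 5 per place) allows for it.
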